A first look on the data before doing the HRQoL analysis will define the cut of point of the analysis according to the following rule. Data obtained from baseline up to 12 months will be analyzed as long as the compliance is at least 50 % in both study arms.

A supplementary analysis will explore potential differences in the HRQoL endpoint between patient with high or low compliance and the dropout rates will be compared between study arms.

Imputation

EORTC QLQ C30/L13

If at least half the items used in a scale are available, the mean scores of these items are imputed to the remaining missing items to calculate the specific scale. If more than half of the items in a scale are missing, this whole scale will be considered missing for the individual patient. This approach (the half rule) is recommended in the EORTC QLQ scoring manual^{5,6}.

Multiple imputation will not be used to adjust for missing data.

Ethics

All patients must give their written consent prior to the study according to local ethical standards and all data will be treated with confidentiality. The study has been approved by the Danish Data Protection Agency. Permissions to withdraw data from DLCR will be obtained.

Both study arms will be offered the CT-scans and clinical evaluations according to standard procedures. In the study presented by Denis et al.², patients in the experimental arm were offered less regular prescheduled CT-scans than control arm, which is not the case in the present study.

Perspectives

The French randomized trial of incorporating PRO data in the follow up of lung cancer patients has shown compelling evidence of a substantial improvement in median and overall survival by using a web-application mediated follow-up⁵. If this Danish adaption of the study shows similar positive results it holds great promise for the future strategy for lung cancer follow-up/response evaluation – and possibly also perspectives for improving follow-up for other cancer patients.

In Denmark there is a unique chance to conduct clinical trials of follow up due to the free and equal access to health care, and the possibility of complete follow up by use of the civil registration number, allowing for linkage between registries, a very low rate of patients lost to follow up and often high completeness of data, leading to good data quality.

The previous Danish findings of the collection of PRO from lung cancer patients across several regions in Denmark²⁹ indicated that lung cancer patients generally had positive feedback about their participation in the project. They felt they made a contribution to their own treatment and follow up, and that the PRO data facilitated their communication with their clinician. The patient felt better prepared for the consultation and that the clinician also had a better idea about their complaints and symptoms. Supported by these data, application of systematically collected PRO data in clinical practice might contribute to better clinical care of Danish patients. If we find similar results as our French colleagues, we might even find a survival benefit. Thus, our hope is to both improve clinical care and survival with the use of PRO data.

The planning of this study is coordinated with the group behind the SUPE-R trial, assessing the benefit of adding PET/CT scans and liquid biopsies in the follow up of patients with stage I-III lung cancer, enabling a comprehensive assessment, standardization and improvement of surveillance of all patients treated for lung cancer in Denmark.

Timetable

The study is expected to begin in January 2018 and end in December 2021. Below is the detailed description of each phase is presented.

January-May 2018	Construction of application
May-July 2018	Feasibility testing
May-July 2018	Data collection plan, including the establishment of a database for data from the study
September 2018	Recruitment of patients begins in Herning
November-December 2018	Recruitment of patients begins in Aarhus and Hillerød
January 2019	Recruitment of patients begins in Aalborg
February-April 2019	Recruitment of patients begins in Herlev and Copenhagen (Rigshospitalet)
Summer/Autumn 2019	Recruitment of patients begins in Sønderborg and Odense
Autumn 2019	Enrollment is competitive and continues until all patients are included.
July-December 2020	Follow up and publication of PhD dissertation and analyses of preliminary findings
December-July 2021	End of study, analyses and publications
2022	Health economic evaluation of the intervention

The final publication with full 24 months follow-up will be expected in the final half of the year 2022.

Feasibility of the project

The project is based in the Regional Hospital in Herning, but the intention is a wide collaboration across hospitals to recruit as many participants as quickly as possible which is also reflected in the broad collaboration of the project group (see organization below).

Implementation of PRO data for clinical practice is complex, both in terms of organization and technology. PRO data system AmbuFlex has already been incorporated in every day clinical practice in the oncology department in Herning, based in the Central Region of Denmark, and is already available in many oncology departments in Denmark, facilitating rapid recruitment and increasing the possibility of successful completion of the project¹⁹.

PRO data collection in oncology departments, where PRO data is not incorporated in everyday practice, will be implemented by using the experience gathered by the collaboration between WestChronic /AmbuFlex and the Danish Cancer Society, where PRO data were collected from lung cancer patients from seven hospitals from different regions in Denmark in 2013-2015²⁹. This project also demonstrated large differences between hospitals, which could be due to differences in regional health-it resources. To ensure fast and reliable implementation, the project will be started stepwise in phases in regions with actual access to AmbuFlex. The pilot phase will be conducted in the oncology department of the Regional Hospital in Herning. The first phase will be started in oncology departments of Central Denmark Region (in Herning and Aarhus), the second phase includes the North Denmark Region (in Aalborg). The third phase will include Region Zealand, and if technically possible, other regions.

Publications

The study will be published after completion, when the final analyses have been performed, in international peer-reviewed journals. The protocol committee writes the first draft and the Vancouver declaration will be followed in all publications based on this study. The names on the author list will be given according to the active participation in the design of the protocol, in the recruitment of patients.

Project organization

The project is intended for a PhD thesis.

Following are members of the protocol committee:

[name] [name], PhD student, West Jutland Hospital, Herning
[name], DMsc., Senior Consultant, West Jutland Hospital, Herning

[name] [name], PhD, Senior Consultant, Professor, University Hospital Aarhus and West Jutland Hospital, Herning

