The randomized clinical trial of adding weekly PRO

Design and setting

The main part of the study consists of a multicenter randomized trial in order to assess the effects of the weekly PRO intervention. The design follows the overall setup presented in the publication by Denis et al, however, adapted to a Danish setting, as described above, including the Danish guidelines for evaluating CT scan in both arms². The randomization and baseline data collection will be made in the IT system (AmbuFlex) by the oncologist at the time of enrollment.

Implementation of the intervention

The intervention is illustrated in Figure 1. *In the experimental arm*, patients will be asked to fill in the PRO questionnaire every week via an internet connection, and they will also be asked to fill in HRQoL questionnaires at any outpatient attendance. However, if their weekly reported symptoms result in a notification, the clinician will contact the patient, and after verification of symptoms, schedule a visit at the clinic for physical examination and evaluation. If relapse or progression of disease is suspected an extra CT scan will be made, otherwise the patient will continue response evaluation/follow-up according to the usual schedule. The clinicians are allowed to reschedule the CT scan based on the phone call alone.

Both the HRQoL measurements and the web application will be administered through a web page that is designed for use on mobile phones, tablets and laptops(AmbuFlex¹⁹). The data will automatically be transferred in real time to a computer server, where notifications are generated and sent to clinicians if the prespecified symptom thresholds are exceeded. Data is automatically scored and will be available in easily interpretable visual reports in the AmbuFlex system.

If participants do not fill in the web-based questionnaire at pre-specified times, a reminder will be sent using a text message to their mobile phone and a message will appear for the clinical staff at the daily notification list.

[figure not shown]

Figure 1. Flow-chart showing the PRO-intervention in the randomized clinical trial.

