To examine the participants quality of life during the study period and at the time of relapse/progressive disease, patients in both arms will be asked to fill in the health-related quality of life (HRQoL) questionnaire every 2 months. The HRQoL questionnaires used are the EORTC QoL-30/LC13 and HADS questionnaire. EORTC-QoL-30 is a questionnaire containing 30 questions with five functional scales (physical function, role function, cognitive function, emotional function and social

function), three symptom scales (tiredness, nausea/vomiting, pain), a global health question and questions regarding frequent symptoms among cancer patients, such as dyspnea, sleep disturbances, loss of appetite, obstipation and diarrhea. The EORTC-QoL-30 also contains a question about financial difficulties. All scales will be linearly transferred to a score between 0-100. For functional scales and global health question, a score of 100 represents the best possible function, while a score of 100 on a symptom scale represents the worst possible symptom. A change in the score by 10 or more is considered a clinically significant change²⁰. LC13 is a supplementary questionnaire to the QLQ-C30 and includes 13 lung cancer-specific questions.

The HADS (The hospital anxiety and depression scale) is a fourteen-item scale. Seven items relate to depression and seven to anxiety. The tool has been developed for detection of anxiety and depression in patients with physical health problems. All items are scored from 0-3 with a possible total score between 0 and 21 for anxiety and depression respectively⁸.

Bjelland et al²¹ identified, in a systematic review, a cut-off point of 8/21 for anxiety or depression. For anxiety, the specificity was 0.78 and the sensitivity 0.9. For depression a specificity of 0.79 and a sensitivity of 0.83 was determined.

The generic EQ-5D-5L⁷ questionnaire will be used to assess quality-adjusted life years (QALY) for a health economic evaluation (*see statistics for details*).

Study design

The study is a multicenter randomised phase III study. After signing informed consent, the patient will be randomized in 1:1 fashion, to the *standard of care arm*, with planned CT-scans according to a standard schedule and measurement of quality of life every 2 months, or to the *experimental arm*, adding weekly PRO monitoring and quality of life measurements to standard of care.

Study population

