Patient enrolment is always when the patients are informed of the results of their first evaluation scan after treatment induction. Patients with stable disease or better response, as described, are eligible.

- In case of treatment end (planned or discontinued) at the time of enrolment, the patient will be included prior to standard follow-up

- In case of ongoing treatment, the patient will be included and continue treatment as scheduled with standard CT based response evaluations
- In the case of local treatment of oligometastatic disease or palliative radiotherapy, the patient will be included if there is no sign of relapse/progression at first evaluation CT scan after treatment and continue follow-up

Inclusion procedure

The patient will have to sign an informed consent at enrolment. The National Committee on Health Research Ethics has been requested and the study does not require approval. Time for consideration before the submission of informed consent is therefore not required and the patient can be enrolled immediately at attendance. Information regarding the study and login procedures for the weekly PRO questionnaire will be provided.

Evaluation criteria

All baseline CT-scans will be evaluated at each site by usual practice. Health-related quality of life (HRQoL) during the observation period will be measured using EORTC QOL-C30/LC13 and HADS. The HRQoL questionnaires including the EQ-5D-5L will be filled in at baseline at randomisation and at every 2 months. The questionnaires will be electronically answered via the AmbuFlex system.

Study plan

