The study plan for the randomized clinical trial is outlined in Table I. In the standard arm, all patients will be followed with CT-scan with the standard of care intervals and asked to fill in the web-based HRQoL questionnaires every 2 months. In the experimental arm, patients will additionally be asked to fill in the web-based PRO questionnaire on a weekly basis. If a detrimental change (See appendix) is noted in the patient's weekly responses to the PRO questionnaire, the patient will be contacted by a study nurse for verification of symptoms. If the symptoms are verified, the patient will be treated by the clinical staff according to standard procedures. If progressive disease is suspected, the patient will have the CT scan rescheduled to as soon as possible. All CT-scans will be described and evaluated by standard practice. It will entirely be up to the treating physician to interpret the results of the CT scans and to define the time of progression as well as the following treatment.

Evaluation at screening, prior to inclusion

The objective of these evaluations is to identify patients, who meet the specified Inclusion- and exclusion criteria. The patient will be informed verbally and in writing. Only patients who have signed informed consent will be included. Following examination and data will be collected prior to inclusion:

- Histological or cytological verification of lung cancer
- Disease stage at treatment start
- Prior treatment and/or maintenance treatment

- Baseline CT scan of the thorax and upper abdomen, showing no signs of progression, after completion of the first treatment for lung cancer, performed within 28 days of randomization.
- Baseline performance status (according to the ECOG's scale¹³), estimated within 14 days of randomization

The patient will be asked to fill in baseline health-related quality of life (EORTC QoL-30/LC13, HADS, EQ-5D-5L) questionnaires via E-Boks immediately after inclusion and then every 2 months.

Additional evaluation for the intervention arm, after inclusion

- Weekly response to the PRO application
- If detrimental changes in PRO responses, earlier evaluation, described above

CT evaluation according to standard follow-up/response evaluation, all participants

- CT-scan of the thorax and upper abdomen, to evaluate the time of progression (or relapse)

Evaluation at relapse or progression

- CT-scan of the thorax and upper abdomen
- Performance status
- Planned 2nd line treatment

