Cost-effectiveness of the PRO application versus standard monitoring is assessed with the incremental cost-effectiveness ratio (ICER), i.e. the ratio of net health care costs to net QALYs (Quality Adjusted Life Years). For a description of the data collection and the analysis, see appendix.

Statistical analysis plan of the Health-Related Quality of Life data

Health-related quality of life (HRQoL) measures are secondary endpoints in the ProWide trial and will be reported in a scientific paper published separately from the main paper. The primary endpoints of the HRQoL paper are Physical function (QLQ-C30), Pain (QLQ C-30), HADS-anxiety and overall EQ-5D-5L index score.

The statistical analyses were planned before any evaluation of the data collected in the trial was made.

Data collection

The HRQoL questionnaires are sent to the patients via the Danish public mail system (eBoks) every second months. All patients in the trial have access to the system. Non-respondents receive a reminder after one week. Responses delivered > 30 days after the invitation is sent is categorized as “missing”.

Specific endpoints of interest in the HRQoL analysis

The specific HRQoL scales that will be analyzed in the ProWide study are:

1. Physical function (QLQ-C30)

Rationale: Physical function is considered a PRO surrogate marker for performance status which is an important prerequisite for both toleration effect of medical antineoplastic treatment.

2. Pain (QLQ C-30)

Rationale: Pain is sensitive to change toward progression in cancer and a symptom that can be managed with analgesics. The symptom could then be improved through actions that are a result of the intervention.

3. HADS-anxiety

Rationale: The intervention could improve the sense of security in the patients and potentially reduce anxiety.

4. EQ-5D-5L index score

Rationale: The generic score represents an overall self-assessed health status and will be used report the effect of the intervention on the overall health.

The EQ-5D-5L score will be reported both in the main paper as a mean-score comparison between the two groups at six months and also analyzed in the HRQoL paper as described below.

HRQoL hypothesis

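### One section asks only the experimental arm for HRQoL forms at any outpatient attendance, against a two-monthly schedule everywhere else, and the SAP does not exclude those forms

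*Combined protocol and SAP*

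**What the plan says.** Implementation of the intervention describes the experimental arm's weekly PRO and adds that "they will also be asked to fill in HRQoL questionnaires at any outpatient attendance". The next sentence says that after a notification the clinician contacts the patient and, once symptoms are verified, will "schedule a visit at the clinic for physical examination and evaluation". No section asks control-arm patients for HRQoL forms at visits.

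The other statements of HRQoL timing are calendar-based:

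- Later in the same section: "patients in both arms will be asked to fill in the health-related quality of life (HRQoL) questionnaire every 2 months".
- Evaluation criteria (main text): the questionnaires "will be filled in at baseline at randomisation and at every 2 months". The synopsis also says every 2 months.
- Study plan: two-monthly HRQoL in the standard arm. For the experimental arm the stated addition is that "patients will additionally be asked to fill in the web-based PRO questionnaire on a weekly basis".
- HRQoL SAP, Data collection: "The HRQoL questionnaires are sent to the patients via the Danish public mail system (eBoks) every second months". The lateness rule runs from the invitation: "Responses delivered > 30 days after the invitation is sent is categorized as" missing.
- Appendix Table 1: quality of life is labelled two-monthly, with no mark under CT evaluation or progression.
- Appendix, sub-study 3: EQ-5D-5L at baseline and every second month.

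Study design is ambiguous. It gives the standard arm quality of life every 2 months and describes the experimental arm as "adding weekly PRO monitoring and quality of life measurements to standard of care", which can be read either as restating the common schedule or as extra HRQoL measurement in one arm.

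**The concern.** The clause on outpatient attendance is a collection rule for one arm only. A site working from that section could hand out forms at visits to experimental patients and not to controls. Some of those visits would exist because the patient had just reported worse symptoms.

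The link to an endpoint is direct for pain. The weekly PRO reuses EORTC items, its pain question is item 9 of the QLQ-C30, and Pain is one of the four HRQoL endpoints. Defining the PRO application says each symptom has a severity threshold. Worse pain could therefore lead to a notification, a visit and an additional Pain measurement, while a control patient with the same course would have no such record.

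The SAP analyses HRQoL with a mixed model and, in support, AUC. It counts compliance as responses over expected responses and uses a 50% floor in both arms to set the analysis cut-off. The main paper reports mean EQ-5D-5L at six months, and the same instrument feeds the QALYs. None of these has a rule for forms that do not answer a two-monthly invitation.

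**Working it through.** **Comparing the sections.** Two-monthly forms and visit forms can both be collected, so the sections are not mutually exclusive. They do disagree on what the experimental arm is asked to do: one clause adds visit forms, while Study plan presents the weekly PRO as that arm's addition.

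**Illustration of size.** The plan gives no figure for this effect and none for alert or visit frequency, so there is nothing to reproduce. Inputs:

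- Scheduled post-baseline forms in 12 months, one every 2 months: 12/2 = 6. The 12-month window is from Compliance and missing data.
- d, the amount by which a visit form is worse than the scheduled course: an assumption. The value 10 borrows the SAP's expected mean deterioration from baseline to progression; 5 and 15 give a range.
- k, extra visit forms per experimental patient: an assumption, 1 to 3.
- MID for physical function and pain: 5 points (Minimal Important Differences).
- No true treatment effect, and no visit forms in the control arm.

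*Simple mean of all post-baseline forms.* Spurious difference = d × k/(6 + k).

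*AUC averaged over 12 months.* Take 60-day intervals over 360 days, linear interpolation, and each extra form in a separate interval. One extra form cuts out a triangle of 0.5 × 60 × d point-days, so the difference = k × 0.5 × 60 × d/360 = k × d/12.

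With d = 10:

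| k | Simple mean | AUC average |
|---|---|---|
| 1 | 10 × 1/7 = 1.4 | 10/12 = 0.8 |
| 2 | 10 × 2/8 = 2.5 | 20/12 = 1.7 |
| 3 | 10 × 3/9 = 3.3 | 30/12 = 2.5 |

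Against the 5-point MID, the simple mean moves by 1.4/5 = 28% to 3.3/5 = 66%, and the AUC average by 0.8/5 = 16% to 2.5/5 = 50%.

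Over d = 5 to 15 and k = 1 to 3, the simple mean ranges from 5 × 1/7 = 0.7 to 15 × 3/9 = 5.0 points. The AUC average ranges from 5/12 = 0.4 to 45/12 = 3.75 points.

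The simple mean is not a planned estimator. AUC is, but only as the supporting analysis. The effect on the mixed model depends on how time and unscheduled forms are coded, which the SAP does not say. With k = 0, that is, with only two-monthly forms analysed, both formulas give 0.

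**The case against.** The strongest reply is that this is a stray clause. The sections that govern HRQoL data describe calendar collection: forms go out by eBoks, the 30-day limit runs from an invitation that a visit form would not have, compliance is assessed at specific time points, and the main-paper EQ-5D-5L comparison sits at a fixed six months. Harm needs two further steps: sites must follow the clause, and the analysts must use the forms. This stands as a limit on likelihood. It does not close the gap, because the SAP only implies that visit forms are left out, and the wording in Study design leaves the clause less isolated than it first looks.

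A reader might infer that the plan samples HRQoL in the experimental arm when patients feel worst. The documents do not support that. Any attendance also covers routine control and treatment visits, and maintenance treatment is allowed. A notification does not automatically lead to a visit: symptoms are verified first, and the CT scan may be rescheduled on the telephone call alone. Repeat notifications for an unchanged symptom are suppressed, except for haemoptysis.

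A reader might also want a firm size, such as a fixed share of records coming from alert visits. No document gives one. The 10-point figure is a mean change up to progression, not a gap between visit forms and scheduled forms, and scheduled scores decline over time as well.

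**Conclusion.** The inconsistency is real, and the collection rule is asymmetric between arms. If it is followed and visit forms are analysed, the likely direction is against the intervention, because the extra records would over-represent symptomatic periods in one arm.

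The size is conditional. The shifts of about 1.4 to 3.3 points (simple mean) and 0.8 to 2.5 points (AUC average) on the QLQ-C30 scales rest on the assumed 10-point gap and 1 to 3 extra forms, and on every extra form being a symptomatic one. Routine-visit forms in the mix would dilute the effect. A reader might extend these figures to all four HRQoL endpoints and the QALYs. That is not supported, since HADS-anxiety and EQ-5D-5L have their own scales and MIDs. Nor do the documents show how far compliance would change, or in which direction.

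The point concerns secondary endpoints and the health economic evaluation. The overall survival analysis is unaffected.

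**What to change.** 1. In Implementation of the intervention, delete the reference to outpatient attendance, so that the section agrees with its own later statement on both arms and with Evaluation criteria, Study plan, the SAP's Data collection and Table 1. In Study design, make clear that HRQoL timing is the same in both arms.
2. Add to the HRQoL SAP: only the baseline form and responses to the two-monthly invitations, issued identically in both arms, enter the mixed model, the AUC, the compliance ratio, the six-month EQ-5D-5L comparison and the QALYs.

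The cost is one deleted phrase, a small clarification and one SAP sentence. The SAP sentence protects the analysis even if some visit forms have already been collected, and it brings the bias from this source to zero.
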